11.1 Primary Endpoint

The primary endpoint is the average palatability rating (on a 1-5 scale) of each treatment combination.

11.2 Secondary Endpoint

Safety, defined by the incidence of grade 2 and above AEs deemed at least probably related to AC by day 12.

12 Statistical Considerations

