1.2 Secondary Objective

Determine the incidence of grade 2 and above SAEs deemed at least probably related to AC.

2 Background and Rationale

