9.1 Event Terminology

Adverse Event: Any untoward medical occurrence associated with the use of a drug in humans, whether or not considered drug related.

Serious Adverse Event: An adverse event is considered "serious" if, in the view of either the investigator or sponsor, it results in any of the following outcomes:

- Death
- A life-threatening adverse experience
- Inpatient hospitalization or prolongation of existing hospitalization
- A persistent or significant incapacity or substantial disruption of the ability to conduct normal life functions
- A congenital anomaly/birth defect
- Important medical events that may not result in death, be life-threatening, or require hospitalization may be considered serious when, based upon appropriate medical judgment, they may jeopardize the patient or subject and may require medical or surgical intervention to prevent one of the outcomes listed in this definition.

Unexpected Event: An adverse event or suspected adverse reaction is considered "unexpected" if it is not listed in protocol-related documents (e.g. protocol, consent documents, investigator brochure, package insert), or is not listed at the specificity or severity that has been observed or given the characteristics of the subject population being studied.

Attribution: is the relationship between an adverse event or serious adverse event and the study drug. Attribution is assigned as follows:

- Definite The AE is clearly related to the study drug
- Probable The AE is likely related to the study drug
- Possible The AE may be related to the study drug
- Unlikely The AE is doubtfully related to the study drug

• Unrelated – The AE is clearly not related to the study drug Attribution must be assigned by the treating physician or the PI.

The following definitions are from the Masonic Cancer Center's Standard Operating Procedure (SOP) Deviation Reporting:

Major Deviation: A deviation or violation that impacts the risks and benefits of the research; may impact subject safety, affect the integrity of research data and/or affect a subject's willingness to participate in the research. Deviations that place a subject at risk, but do not result in harm are considered to be major deviations.

Minor Deviation: A deviation or violation that does not impact subject safety, compromise the integrity of research data and/or affect a subject's willingness to participate in the research.

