9.2 Event Documentation

Participants will be monitored for adverse events from the 1st dose of study treatment through day 12. After that time point, events meeting the definition of serious and at least possibly related to study treatment will be documented upon knowledge.

We will collect the following Grade 2-5 adverse events attributable to AC:

Aspiration of activated charcoal

In addition any event meeting the definition of a serious adverse event (SAE) regardless of attribution that occurs during this period will be documented in the source document and recorded in OnCore.

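### The only defined safety endpoint leaves out grade 2 or higher events rated 'possibly' related to AC, and no other safety summary is planned that would show them

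*Combined protocol and SAP*

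**What the plan says.** Section 11.2 defines the secondary endpoint as "Safety, defined by the incidence of grade 2 and above AEs deemed at least probably related to AC by day 12". Section 1.2 uses the same attribution threshold but a different class of event: "Determine the incidence of grade 2 and above SAEs deemed at least probably related to AC".

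Section 9.1 sets out five attribution levels, from definite to unrelated, assigned by the treating physician or the PI. The lowest level that 11.2 counts reads "Probable The AE is likely related to the study drug". The next one down reads "Possible The AE may be related to the study drug".

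On detection, sections 3 and 6.2 have the study team contact subjects after each round of dosing and screen for grade 2 or higher AEs and for SAEs, with no attribution filter. On recording up to day 12, section 9.2 says "We will collect the following Grade 2-5 adverse events attributable to AC", and the list that follows has one entry, aspiration. For serious events in the same period it says "any event meeting the definition of a serious adverse event (SAE) regardless of attribution that occurs during this period will be documented".

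Section 12.3 deals only with the palatability ratings. The protocol gives no reason for choosing 'at least probably', and it plans no safety summary at any other attribution level.

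**The concern.** The toxicities that the protocol expects are nausea and vomiting (6.3) and vomiting, diarrhea and constipation (8.1.7). Healthy people have these symptoms for many ordinary reasons. Every volunteer takes AC in both weeks (Table 1 in 6.1.1), so there is no AC-free period or group against which to judge a single episode. An assessor who sees one grade 2 gastrointestinal event could reasonably call it possible rather than probable, and under 11.2 that event would not count.

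The study is described as a test of tolerability and safety (12.1), and section 2.4 says that the palatability and tolerability findings will help in designing later trials in patients. Someone planning such a trial would see one incidence figure. They would have no means of telling whether a low count meant few events or a number of events rated possible.

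**Working it through.** **Step 1. Which ratings count.** Sections 9.1 and 11.2 side by side, for grade 2 or higher AEs by day 12:

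| Attribution (9.1) | Counted under 11.2 | Counted at 'at least possibly' |
|---|---|---|
| Definite | yes | yes |
| Probable | yes | yes |
| Possible | no | yes |
| Unlikely | no | no |
| Unrelated | no | no |

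The two definitions differ by the 'possible' row and nothing else.

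**Step 2. Denominators.** There are 12 subjects (synopsis, section 3). Table 1 gives 12 subjects × 2 periods = 24 assignments over 4 combinations, and 24 / 4 = 6. This reproduces the six subjects per combination stated in 12.1. Taking incidence as the share of subjects with at least one counted event, one subject whose only qualifying event is rated possible changes the figure by:

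- overall: 1/12 = 8.3 percentage points
- within one combination, if tabulated that way: 1/6 = 16.7 percentage points

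**Step 3. Direction.** Let p be the share of subjects with a grade 2 or higher event rated at least possible, and q the share of those subjects whose highest rating is only possible. Then:

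- incidence at 'at least possibly' = p
- incidence under 11.2 = p × (1 − q)
- difference = p × q, which is zero or positive

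The figure under 11.2 can equal the wider one or fall below it. It cannot exceed it.

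**Step 4. Size.** The documents give no value for q. They give no value for p at these doses either. The one rate available is 15–27% for nausea/vomiting in section 6.3; it comes from poisoning treatment and carries no grade. Even if it were borrowed for p, letting q run over its full range gives:

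- p = 15%: from 15% × (1 − 0) = 15% down to 15% × (1 − 1) = 0%
- p = 27%: from 27% × (1 − 0) = 27% down to 27% × (1 − 1) = 0%

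Everything from no effect to complete loss is compatible with the documents. A narrower range would only restate an assumed q.

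**Step 5. Would the wider counts be available?** Take a non-serious grade 2 episode of vomiting on day 2.

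- Sections 3 and 6.2: it falls within the screening.
- Section 9.2: it is not aspiration, so it is not on the list of events to collect. It is not serious, so the SAE rule does not capture it.
- Section 11.2: it counts if rated probable or definite.
- Section 1.2: it does not count at any rating, because it is not an SAE.

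As 9.2 is written, the event may not be recorded at any attribution level. Changing the threshold in 11.2 alone would not deliver the wider counts.

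**The case against.** The strongest defence is that this is a descriptive secondary endpoint in a 12-person palatability pilot, and that 'at least probably' trades sensitivity for specificity on purpose. With no AC-free control, some events rated possible will have nothing to do with AC, so the wider count may overstate AC-related incidence just as the narrower one may understate it. Lowering the cut also leaves a subjective judgement in place and only moves it to the boundary between possible and unlikely. All of this stands. It means that neither count can be called the true incidence, and it is the reason to show several counts rather than replace one by another. It does not supply the missing rationale for the threshold or a summary of what the threshold leaves out.

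A reader might go further in three ways that the documents do not support.

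- *That 9.2 contradicts 11.2.* After day 12, "events meeting the definition of serious and at least possibly related to study treatment will be documented upon knowledge". This is a documentation rule for serious events in a later window, and 11.2 is an endpoint for AEs up to day 12. For serious events, documentation is in fact wider during the dosing period, when attribution plays no part.
- *That the lack of masking is the problem.* Every subject takes AC in both weeks, so hiding the dose or solution would not hide exposure to AC.
- *That events rated possible vanish from the trial.* They are left out of the endpoint. Staff still screen for all grade 2 or higher AEs, SAEs to day 12 are recorded whatever the attribution, and the rating form in Appendix II asks subjects about issues they think may be related.

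**Conclusion.** The point holds as a limitation of the endpoint definition. Grade 2 or higher events rated possible are excluded from the only defined safety endpoint, no stated reason supports the exclusion, and 12.3 plans nothing that would reveal it. The reported incidence may be lower than an 'at least possibly' incidence.

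It would be too strong to say that the incidence *is* understated. That would require such events to occur, to be rated possible, and to be caused by AC, and the documents establish none of these. The gap is p × q with both terms unknown, and it may be zero. The only firm sizes are the steps of 8.3 points overall and 16.7 points within a combination per subject concerned. They assume that incidence is counted per subject and that the subject has no other event that already counts.

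The primary palatability comparison is not affected. Nor is the sample size, which 12.2 bases on balance across combinations alone.

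**What to change.** In 11.2, report the incidence of grade 2 or higher AEs by day 12 at 'at least possibly' related to AC, and show the counts at 'at least probably' and regardless of attribution beside it. Add the same three rows to 12.3 so that the summary is planned.

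In the same amendment:

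- reconcile 1.2, which says SAEs, with 11.2, which says AEs;
- reconcile 9.2, which lists only aspiration for collection, with sections 3 and 6.2, which screen for all grade 2 or higher AEs, so that the events these counts need are recorded with their attribution.

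The screening contacts and the five-level scale are already in the protocol, so no visits or subjects are added. The work is the amendment, together with recording and attributing whatever non-serious grade 2 or higher events the screening finds. The downside is a possibly less favourable headline figure that includes some background events. Showing the three counts together makes that visible, and the figure that 11.2 now defines is still reported.

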12.1 Study Design

This is a pilot study designed to test tolerability and safety of oral AC in 12 healthy volunteers.

We will follow a predetermined treatment assignment using the balanced incomplete block design shown in Section 6.1.1. Twelve healthy subjects will be assigned two dose and solution combinations to take for three days each. Each subject will receive each dose once and each solution once. Different subjects will receive different combinations or different sequences. Each of the four combinations will be given to six subjects total, allowing straightforward comparisons. Each solution (or dose) precedes each of the others for exactly half of the subjects, to minimize confounding due to the ordering of the treatment assignments.

12.2 Sample Size Considerations

The sample size was chosen so that each combination could be given the same number of times.

12.3 Statistical Analysis

We will average each subject's score over the 3 days of each treatment. If a subject misses one or more days, we will impute the average of the known days for the unknown days. We will also record the reported reason for not taking AC, and based on that we may adjust the imputation procedure on a case-by-case basis. Since the goal is to pick the most tolerable/palatable combination, we will choose the one with the highest average score; no statistical hypothesis tests are required. We will also consider the combination with the fewest percentage of

"terrible" or "bad" ratings, although this is expected to be associated with average score.

13 Ethical and Regulatory Considerations

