1.1 Primary Objective

The primary objective is to compare 2 extemporaneously prepared Medical Grade Activated Charcoal, "AC" suspensions at 2 doses (4 combinations in total) in healthy volunteers for palatability/tolerability.

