2.4 Rationale

Investigators are looking for new ways to protect the microbiome during the period of antibiotic exposure, improve the safety of antibiotics and reduce the rate of dysbiosis-related complications in patients. Determining the palatability and tolerability of AC in healthy volunteers in this research will aid in the design of future trials to investigate the efficacy of AC in patients.

3 Study Design

We will use the powder form of medical grade oral AC and mix it with liquids for administration. 12 healthy volunteers will be enrolled to determine the two most palatable and tolerable AC combinations. There will be a total of 4 combinations (2 AC doses and 2 solutions) in stage 1. Each participant will drink an assigned combination every day for 3 consecutive days (Monday, Tuesday, Wednesday, "M/T/W") and switch to a different assigned combination M/T/W the following week. AC solution assignments will be defined before the study using a balanced incomplete block design. Each subject will rate their experience using a 5-point scale every day for the 12 days they are on study.

The following outcome variables will be measured:

- (i) Each healthy volunteer will rate their experience using a 5-point scale (1=terrible, 2=bad, 3=okay, 4=good, 5=great) every day.
- (ii) To evaluate tolerability, after each round of study product consumption, a member of the study team will contact the subject and screen for grade 2 or higher AEs and SAEs

4 Participant Selection

Study entry is open to adult volunteers regardless of gender or ethnic background. While there will be every effort to seek out and include women and minorities, the subject population is expected to reflect the population of Minnesota.

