6.1.3 Experience Rating

After drinking the solution, each subject will rate their experience using a 5-point scale (1=terrible, 2=bad, 3=okay, 4=good, 5=great) every day (Appendix III). They will be asked to do this daily starting day 1 (Mon of week 1) through day 12 (Friday of week 2).

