Appendix II – Volunteer Product Rating Form

Study	ID:
Date:	
1.	Please rate your charcoal experience today by choosing one the 5 items below
	1 2 3 4 5
2.	Have you had any issues since last drink of charcoal that you think may be related to your charcoal experience?

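### Section 12.3 chooses the best tolerated and most palatable combination on drinking-day ratings; adverse events and form question 2 are neither tabulated by combination nor used in the choice

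*Combined protocol and SAP*

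**What the plan says.** - **Objective.** Section 1.1 compares the combinations "in healthy volunteers for palatability/tolerability". Section 3 seeks the two best combinations on both qualities.
- **Two outcomes.** Section 3 lists the 1-5 rating first and then a separate measure: "To evaluate tolerability, after each round of study product consumption, a member of the study team will contact the subject", to screen for grade 2 or higher AEs and for SAEs.
- **Endpoints.** Section 11.1: "The primary endpoint is the average palatability rating (on a 1-5 scale) of each treatment combination". Section 11.2 makes grade 2+ AEs at least probably related to activated charcoal (AC) a secondary safety endpoint, not broken down by combination.
- **Selection rule.** Section 12.3 averages each volunteer's score over the three days of each treatment and then states: "Since the goal is to pick the most tolerable/palatable combination, we will choose the one with the highest average score". It will also look at the percentage of 'terrible' or 'bad' ratings, "although this is expected to be associated with average score".
- **Missed days.** Section 12.3 fills a missed day with the mean of the known days. The reason for not taking AC is recorded and may change the imputation case by case; no rule is given.
- **Rating form.** Section 6.1.3: "After drinking the solution, each subject will rate their experience using a 5-point scale". Appendix II asks for a rating of that day's charcoal experience and then, as question 2: "Have you had any issues since last drink of charcoal that you think may be related to your charcoal experience". Sections 11 and 12 do not mention question 2.

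**The concern.** The plan defines tolerability by one measure and then claims it from another. Section 11.1 itself calls the score a palatability rating, yet section 12.3 treats the top scorer as the best tolerated as well. The second criterion adds no independent information, because it re-expresses the same ratings.

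Followed as written, the rule could name a combination most tolerable although more of its volunteers were unwell after drinking it, and no planned table would show this. Section 2.4 says the results will help design later efficacy trials in patients, so an unsupported label would carry forward.

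**Working it through.** **Allocation (the plan's own figure).** Section 12.1 gives six volunteers per combination. From Table 1: 12 volunteers × 2 periods / 4 combinations = 6, with each combination given three times in week 1 and three times in week 2. The figure reproduces. Sections 12.1 to 12.3 contain no power calculation, SD or margin to check.

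**What can reach the score.** Sections 6.1.3, 7 and 12.3 and Appendix II, read together:
- Prompt effects of any drink, before that day's form is completed: yes.
- Lasting or next-day effects of drinks 1 and 2: yes, through the Tuesday and Wednesday ratings.
- Effects that follow the third drink, once Wednesday's form is done: no. The Thursday and Friday calls may find them, but only the three treatment days are averaged.
- Illness that makes a volunteer skip a day: not under the default; only through the undefined case-by-case adjustment.

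**Size of the imputation effect (illustration).** A volunteer scores 4 on day 1, then stops because of vomiting.
- Default: (4 + 4 + 4)/3 = 4.0.
- Missed days scored 1: (4 + 1 + 1)/3 = 2.0.
- Shift in the combination mean: (4.0 − 2.0)/6 = 0.33 points.

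**How often there would be something to report.** Section 6.3 gives nausea/vomiting of 15-27% at poisoning doses, which it describes as much higher than those planned here. I use that range, and a lower 5-10%, purely as assumptions.
- Expected number of six affected: 6 × 0.15 = 0.9 to 6 × 0.27 = 1.6.
- P(at least 1 of 6) = 1 − (1 − p)^6: 0.62 at 15%, 0.85 at 27%; 0.26 at 5%, 0.47 at 10%.

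**How precise the counts would be.**
- With 0/6 affected, the one-sided 95% upper bound is 1 − 0.05^(1/6) = 0.39.
- For two independent groups of six with equal true rates, the chance that a given one has the worse count is (1 − Σ f(k)²)/2, where f is the binomial(6, p) probability. At 15% this is (1 − 0.334)/2 = 0.33; at 27% it is (1 − 0.257)/2 = 0.37. Independence is assumed. In Table 1, A1 and B2 go to the same six volunteers, as do A2 and B1, so those two comparisons would differ.

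**Text conflicts that the tolerability data depend on.**
- AEs: sections 3 and 6.2 screen for grade 2 or higher events generally; section 9.2 lists only aspiration among the grade 2-5 attributable events to be collected, plus all SAEs.
- Rating days: sections 3 and 6.1.3 have ratings every day through day 12; section 7 has Monday to Wednesday only. If section 7 governs, a week-1 effect after the third drink can still appear on the week-2 Monday form, but the same effect in week 2 has no later form to appear on.

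**The case against.** The strongest reply is that the item rates the whole experience of the day, not taste, so the score already carries some tolerability. That stands. A reader might infer that the score is blind to tolerability; the documents do not support this, since prompt effects and next-day effects of the first two drinks can lower it. What the reply does not cover is anything after the third drink, or the fact that section 3 gives tolerability its own measure.

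Three further replies stand in part:
- *Intolerance can enter through the reason for a missed dose.* It can, but at discretion, without a rule, and only for volunteers who miss a day.
- *AEs are not ignored.* Correct: related grade 2+ events are the secondary endpoint. They are not planned by combination and have no link to the choice.
- *The data may not be in hand.* A reader might infer that everything needed is already collected. Section 9.2 leaves this open: if it governs, non-serious gastrointestinal events would not be recorded as AEs.

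It can also be said that counts out of six cannot rank combinations. That is right, and it rules out a rule such as requiring the winner's count to be no worse than the runner-up's: by chance alone the winner would fail about 33-37% of the time under the assumptions above. It does not argue against showing the counts.

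**Conclusion.** The concern holds in a limited form. The choice rests on the three-day mean score and a second summary of that same score. The plan's named tolerability measure and form question 2 play no part in it and are not summarised by combination. The score supports a statement about palatability and reflects tolerability only in part.

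The illustrated effect is 0.33 points on a six-person mean for one volunteer who stops after scoring 4, assuming default imputation and a score of 1 as the comparison. The documents do not show that the wrong combination would be chosen, and a reader should not infer that: the 15-27% rate comes from higher doses, and nothing says how AEs and scores would be related. Nor do they support a formal tolerability ranking, given the 39% upper bound at 0/6. What changes is the conclusion the trial may draw. Sample size is unaffected.

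**What to change.** 1. **Reconcile first.** Bring sections 3 and 6.2 (all grade 2+ AEs) into agreement with section 9.2 (aspiration only), and sections 3 and 6.1.3 (ratings through day 12) with section 7 (Monday to Wednesday).
2. **Add one table to section 12.3.** Next to the mean score, give for each combination (n=6) the number of volunteers with any issue reported on question 2, any grade 2+ AE found at the contacts, and any AC day missed because of intolerance.
3. **State the attribution rule in advance.** Assign each event to the combination last taken before it. A week-2 Monday answer about the time since the last drink then counts for the week-1 combination; assignment by calendar week would misplace it.
4. **Limit the label.** Call the score-based winners, including both of the two sought in section 3, most palatable. Report tolerability descriptively beside them, with no gate or test.

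The cost is one table and a few sentences, with no change to the 12 volunteers. The downside is imprecise counts and a more cautious label.
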